Objectives: The primary efficacy objective is to compare the effect of the individualised treatment plan, relative to a minimal physiotherapeutic rehabilitation program, on changes in Shoulder Pain and Disability Index (SPADI) from baseline to 12 weeks after initiating the treatment, in women with late-term shoulder impairments after primary breast cancer surgery.

Methods: The study was designed as a randomised trial with a two-group comparison testing superiority hypothesis related to the primary and key secondary objectives. In total, 130 participants would randomised (allocation 1:1) to either an expert assessment of shoulder impairments followed by an individualised treatment plan or to follow a minimal physiotherapeutic rehabilitation program delivered in a pamphlet. The primary analysis will be based on the Intention to Treat (ITT) population; the ITT principle asserts the effect of a treatment policy (that is, the planned treatment regimen), rather than the actual treatment given (i.e., it is independent of treatment adherence). The analyses of the key secondary outcomes will be performed in a prioritized order. The analyses of the confirmatory secondary outcomes will be performed in sequence until one of the analyses fails to show the statistically significant difference, or until all analyses have been completed at a two-sided statistical significance level of 0.05. The continuous outcomes will be analysed based on Repeated-Measures Mixed Effects Models (time: 0, 4, 8, and 12 weeks from baseline).

Registration: ClinicalTrials.gov, identifier: NCT05277909. Registered on 11 March 2022.

INTRODUCTION

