The primary aim of this trial is to compare the effectiveness of an individualised treatment, relative to a minimal home-based program, on changes in Shoulder Pain and Disability Index (SPADI) from baseline to week 12 after initiating the treatment, in women with late-term shoulder impairments after breast cancer surgery.

The null hypothesis is that there is no difference in SPADI between the two groups. The alternative hypothesis is that women randomised to the individualised treatment (*Intervention group*) will improve more in shoulder function and reduce shoulder pain 12 weeks after initiating the treatment than those randomised to the minimal home-based program (*Control comparator group*).

Objectives

Primary efficacy objective:

To compare the effect of the individualised treatment plan, relative to a minimal physiotherapeutic rehabilitation program, on changes in Shoulder Pain and Disability Index (SPADI) from baseline to 12 weeks after initiating the treatment, in women with late-term shoulder impairments after primary breast cancer surgery.

Key secondary objectives:

To compare the effect of the individualised treatment plan, relative to a minimal physiotherapeutic rehabilitation program, after 12 weeks on changes in the following key secondary outcome measures:

- SPADI pain,
- SPADI function,
- SPADI clinical response,
- Impression of the treatment's success,
- Active Range of Motion (A-ROM),
- Passive Range of Motion (P-ROM),
- Number of treatments received due to shoulder symptoms,
- Maximum shoulder pain intensity,

- Shoulder pain during general activities,
- Shoulder pain at rest,
- Shoulder pain during sleep, and
- Shoulder pain during flexion/rotation/abduction.

Exploratory objectives covered will be published in secondary papers covering the following:

To compare the effect of the individualised treatment plan, relative to a minimal physiotherapeutic rehabilitation program, after 12 weeks on changes in:

- Pain medication consumption,
- Depression score (PHQ-9), and
- Anxiety score (GAD-7).

STUDY METHODS

Trial design

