This trial is designed as a stratified (by type of surgery and radiotherapy), block randomised (1:1 allocation), controlled, parallel group and assessor-blinded, single-centre superiority trial conducted in Denmark. Women are recruited from an earlier letter inquiry, based on a register extract, including an invitation to participate in a cross-sectional survey of late-term effects. Women reported shoulder impairments invited to participate in this trial and randomised to an expert assessment of shoulder impairments with an individualised treatment plan or to a 12 week home-based program, which is a minimal intervention within the physiotherapeutic rehabilitation and is delivered in a pamphlet. The two interventions are more described specifically in the trial protocol. The primary endpoint will be assessed at the 12 weeks follow-up, while many of the outcome measures are also collected at 4 and 8 weeks follow-up.

The SAP is reported in accordance with the “*Guidelines for the Content of Statistical Analysis Plans in Clinical Trials*” (2). The trial was registered prior to First Patient First Visit at ClinicalTrials.gov (NCT05277909) and follow the principles of the Declaration of Helsinki (3). The recruitment period started in April 2022 (i.e. First Patient First Visit), and expected to be completed in August 2022 (i.e. Last Patient First Visit).

Randomisation, allocation concealment, and blinding

Eligible participants were randomly assigned in permuted blocks of 2 to 6, with a 1:1 allocation, based on a computer-generated randomisation list generated by an independent data manager implemented into the REDCap randomisation system (4), to either *Intervention group* or *Control group*. Participants were stratified in 5 groups according to type of surgery and +/- radiotherapy treatment:

1. Breast Conserving Surgery (BCS) and Sentinel Lymph Node Dissection (SLND) + radiotherapy;
2. BCS and SLND – radiotherapy;
3. BCS and Axillary Lymph Node Dissection (ALND) + radiotherapy;
4. Mastectomy and SLND – radiotherapy; and
5. Mastectomy and ALND + radiotherapy)

Immediately after obtaining the written informed consent, the baseline measures and outcomes will be collected. The outcome assessors who performed the clinical baseline assessment will also perform the 12-week follow-up, blinded towards treatment allocation. Participants were informed about their group allocation directly after randomisation.

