The overview of the trial time-points of each outcome assessment is presented in the **Table 1** in the study protocol at the TRIALS journal (<https://doi.org/10.1186/s13063-022-06659-1>): “*Effectiveness of an expert assessment and individualised treatment compared with a minimal home-based exercise program in women with late-term shoulder impairments after primary breast cancer: Study protocol for a randomised controlled trial*”. The intervention start date (*Intervention group* or *Control comparator group*) for each patient is used to calculate the 4-, 8-, and 12-weeks follow-up time points.

STATISTICAL PRINCIPLES

Confidence intervals and p-values

All 95% confidence intervals (95% CIs), and *P-values* will be two sided. Adjustments for multiplicity will not be applied, but rather the analyses of the key secondary outcomes will be performed and interpreted in a prioritized order. The analyses of the confirmatory secondary outcomes will be performed in sequence until one of the analyses fails to show the statistically significant difference, or until all analyses have been completed at a statistical significance level of 0.05. The key secondary statistical tests will be reported with *P* values for hypothesis tests and claims of statistical significance.

Analysis populations

The primary analyses will be based on the Intention to Treat (ITT) population, i.e., based on the Full Analysis Set (having the outcome of interest measured at baseline). The ITT principle asserts the effect of a treatment policy (that is, the planned treatment regimen), rather than the actual

treatment given (i.e., it is independent of treatment adherence). Accordingly, participants allocated to a treatment group will be followed up, assessed and analysed as members of that group, irrespective of their adherence to the planned course of treatment (i.e., independent of withdrawals and cross-over phenomena) (8).

TRIAL POPULATION

Screening data

The total number of patients, screened for eligibility, will be collected, and presented in a CONSORT Flow Diagram ([Figure 1](#)) for documenting the flow of participants through the trial. The number of ineligible patients randomised by mistake, if any, will be reported including reason for ineligibility.

Eligibility criteria

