- *Passive Range of Motion (P-ROM) [Time Frame: 0 and 12 weeks]*

A key secondary outcome will be the between-group difference in change in P-ROM degrees ($\Delta P-ROM_{12} = P-ROM_{12\text{-weeks follow-up}} - P-ROM_{\text{baseline}}$) from baseline to 12 weeks after initiating the treatment. The smartphone inclinometer (GetMyROM) is considered valid and reliable to assess A-ROM in flexion, internal rotation, external rotation and abduction (17-21).

- *Number of treatments received due to shoulder symptoms [Time Frame: 12 weeks (follow-up)]*

A key secondary outcome will be the between-group difference in mean number of treatments received due to shoulder symptoms from baseline to 12 weeks after initiating the treatment.

- *Maximum shoulder pain intensity [Time Frame: 0, 4, 8 and 12 weeks]*

A key secondary outcome will be the between-group difference in change in maximum pain intensity ($\Delta MaxPain_{12} = MaxPain_{12\text{-weeks follow-up}} - MaxPain_{\text{baseline}}$) from baseline to 12 weeks after initiating the treatment. The Numeric Rating Scale (NRS) is considered a valid, reliable and responsible single 11-item patient-reported pain scale that ranges from 0 (no pain) to 10 (worst pain) (22).

- *Shoulder pain during general activities [Time Frame: 0, 4, 8 and 12 weeks]*

A key secondary outcome will be the between-group difference in change in shoulder pain during general activities ($\Delta General\ activity\ pain_{12} = General\ activity\ pain_{12\text{-weeks follow-up}} - General\ activity\ pain_{\text{baseline}}$) from baseline to 12 weeks after initiating the treatment. The NRS is considered a valid, reliable and responsible single 11-item patient-reported pain scale that ranges from 0 (no pain) to 10 (worst pain) (22).

- *Shoulder pain at rest [Time Frame: 0, 4, 8 and 12 weeks]*

A key secondary outcome will be the between-group difference in change in shoulder pain at rest ($\Delta Pain\ at\ rest_{12} = Pain\ at\ rest_{12\text{-weeks follow-up}} - Pain\ at\ rest_{\text{baseline}}$) from baseline to 12 weeks after initiating the treatment. The NRS is considered a valid, reliable and responsible single

11-item patient-reported pain scale that ranges from 0 (no pain) to 10 (worst pain) (22).

- *Shoulder pain during sleep [Time Frame: 0, 4, 8 and 12 weeks]*

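### The number of shoulder treatments received is tested in the confirmatory sequence without a counting rule or a favourable direction, and is listed ahead of five pain outcomes

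*SAP*

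**What the plan says.** - **Hypothesis.** The abstract describes a two-group comparison "testing superiority hypothesis related to the primary and key secondary objectives". The Objectives section compares the two programmes "after 12 weeks on changes in the following key secondary outcome measures", and the list that follows includes "Number of treatments received due to shoulder symptoms".
- **Outcome.** Under Key secondary outcomes the SAP writes: "A key secondary outcome will be the between-group difference in mean number of treatments received due to shoulder symptoms from baseline to 12 weeks". The window runs from the start of treatment. Treatment given under the allocated plan is not excluded, and no favourable direction is stated.
- **Arms.** Under Trial design, women are "randomised to an expert assessment of shoulder impairments with an individualised treatment plan or to a 12 week home-based program". The home programme comes as a pamphlet. Further description of both interventions is left to the protocol.
- **Testing rule.** Under Confidence intervals and p-values, "the analyses of the key secondary outcomes will be performed and interpreted in a prioritized order". The confirmatory secondary outcomes are "performed in sequence until one of the analyses fails to show the statistically significant difference". Tests are two-sided at 0.05, and key secondary tests are reported with P values and claims of significance. The same paragraph uses both the key and the confirmatory label, and the SAP has no separate confirmatory list.
- **Order.** The objectives list, the outcome definitions, Table 2 and Appendix Tables 1 to 3 all put the count after passive range of motion (P-ROM) and before maximum shoulder pain intensity. Table 2 reports it in a column whose heading speaks of mean improvement.

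**The concern.** One arm is allocated an assessment and a treatment plan, the other a pamphlet. A count of shoulder treatments over the same 12 weeks, taken as written, includes what the first arm was allocated to receive. The rule for moving on asks only for significance on a two-sided test. A significant excess of treatments in the intervention arm would therefore pass the step and be reported as a confirmatory result, although it may show only that the plan was carried out. If the authors meant care sought outside the trial, the item is a health-care-use measure. The SAP does not say whether less or more of such care would be the success.

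The second issue is position. In the listed order, this step determines whether maximum pain, pain during general activities, pain at rest, pain during sleep and pain on movement can support a confirmatory claim. Whether it passes depends on how treatments are counted and how much care each arm receives, not on whether pain improved.

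**Working it through.** **1. Position.** The listed order is: (1) SPADI pain, (2) SPADI function, (3) SPADI response, (4) global perceived effect, (5) active range of motion, (6) P-ROM, (7) number of treatments, (8) maximum pain, (9) general activities, (10) rest, (11) sleep, (12) flexion/rotation/abduction. Six tests must succeed before the count is tested, and 12 − 7 = 5 pain outcomes follow it.

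**2. The plan's own figure.** The SAP gives no mean, SD or power for the count. Its only size calculation is for total SPADI: difference 8, SD 15.41, two-sided 0.05, power 85%. The normal approximation gives 2 × (1.960 + 1.036)² × (15.41/8)² = 66.6, or 67 per arm against about 65 stated. Power at 65 is 0.841. That is close, and nothing here turns on it. I use 65 per arm as the planned size.

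**3. If allocated treatment is counted.** Assumptions: outside care is equal, the intervention arm receives d more treatments on average, and the SD of the count is 2 to 4. None of these comes from the SAP. For a two-sample t-test with 128 degrees of freedom:

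- Smallest significant observed difference = 1.979 × SD × √(2/65), which is 0.69, 1.04 and 1.39 treatments for SD 2, 3 and 4.
- Noncentrality = d / (SD × √(2/65)). For d = 2 this is 5.70, 3.80 and 2.85.

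| Extra treatments (d) | SD 2 | SD 3 | SD 4 |
|---|---|---|---|
| 0 | 5% | 5% | 5% |
| 1 | 81% | 47% | 29% |
| 2 | over 99% | 97% | 81% |

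Smaller arms lower these values. For illustration, 15 per arm and d = 2 give 75%, 42% and 26%.

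**4. If only outside care is counted.** With no true difference between the arms the step passes with probability 0.05, so it stops the chain with probability 1 − 0.05 = 0.95, whatever happens to pain.

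**5. Conditioning.** The figures in steps 3 and 4 apply to step seven once it is reached. They also assume that the count's result does not depend on the six earlier results. If P6 is the probability that all six succeed, the overall probability that this step blocks the five pain outcomes under step 4 is P6 × 0.95. The SAP gives nothing from which to compute P6.

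**6. After the change.** With the count removed, 12 − 1 = 11 outcomes remain and P-ROM leads directly to maximum pain. No sample size changes.

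**The case against.** Several points against the concern are sound.

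- A reader might conclude that the test measures delivery and not benefit. The SAP does not establish that. It leaves the counting rule open and refers to the protocol for the interventions, and the number of sessions is not given. If only outside care is counted, the item is not delivery at all. What stands is that the definition as written excludes nothing and names no direction.
- A reader might take the 81% to over 99% as the chance of a spurious confirmatory claim in a trial with no benefit. It is not. With no effect on pain, SPADI pain at step one passes only about 5% of the time, so step seven would rarely be reached. The 95% has the same condition: six earlier successes.
- A reader might infer inflated type I error. A fixed sequence keeps the familywise rate at 0.05 even when one step is trivially non-null, and the pain tests after it remain valid.
- Pain is not left untested. SPADI pain is first in the list and this step does not touch it.
- No sentence says that the listed order is the test order. It is a strong inference, because a prioritised order is announced and every list agrees. If it is wrong, the place of the count in the sequence is undefined.

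These points limit the size of the problem. They do not supply the counting rule or the direction, and they do not explain why a measure of care received should stand ahead of five pain outcomes.

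**Conclusion.** The concern holds in a limited form. The SAP places a count of treatments in a confirmatory superiority sequence without saying what is counted or which direction is favourable. Neither plausible reading gives a clean efficacy result: one includes treatment allocated to a single arm, the other is health-care use. If the listed order is the test order and the six earlier tests succeed, this step decides whether five pain outcomes can carry a confirmatory claim, on grounds unrelated to efficacy. Its conditional size runs from a 95% chance of stopping the chain (only outside care counted, no true difference) to about 81% to over 99% for opening it (allocated treatment counted, 2 extra treatments). Those opening probabilities rest on an assumed SD of 2 to 4 and 65 per arm. The harm is to interpretation and to possible blocking, not to error control. The point should be settled before unblinding, and it does not threaten the primary analysis.

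**What to change.** Before unblinding, take the number of treatments out of the confirmatory sequence, so that P-ROM is followed directly by maximum shoulder pain intensity. Amend the key secondary list, the multiplicity paragraph and Table 2 to match, and state there that the listed order is the test order. Report the count descriptively by arm, split into treatment under the allocated plan and shoulder treatment obtained elsewhere where the source was recorded. Where it was not recorded, report the total.

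The minimum alternative is to place the count last. That removes the blocking, but the SAP must then still say what is counted and which direction is favourable.

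The cost is a wording change and a table edit. One planned outcome loses its confirmatory P value, eleven remain in sequence, and the sample size is unchanged.

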To ensure concealment, the primary investigator, assessors and administrators of the randomisation were blinded to the block sizes, as the randomisation code was stored in REDCap, with no access for the project group.

Sample size and power considerations

The sample size and power estimation were based on the expected between-group difference in the change in SPADI score from baseline to the 12 weeks follow-up. In order to achieve an *a priori* statistical power of at least 85%, with a two-sided significance level $\alpha=0.05$, with an anticipated standard deviation (SD)=15.41 SPADI units (5), the estimated total sample size was n=130 (~ 65 participants in each group), to be able to detect a minimal clinically relevant difference defined as 8 points on the SPADI-score (6,7).

[figure not shown]
Correction:

In the study protocol we estimated an eligible population of approximately n=384 women willing to participate (<https://doi.org/10.1186/s13063-022-06659-1>), based on the cross sectional survey sent to

Individualised treatment vs. a home-based exercise program in women with late-term shoulder impairments after primary breast cancer surgery

approximately 4.300 women in Region of Southern Denmark, corresponding to an expected eligible population rate of 8%.

In fact, we sent out the questionnaire to 9.934 women nationwide, and obtained a participation rate of 56.7% in the cross sectional survey. For the Region of Southern Denmark we received 1.164 complete replies. Of these only 129 women matched the inclusion and exclusion criteria, and furthermore, 76% of these eligible women declined the offer to participate, resulting in $n=31$, corresponding to a much lower than expected, eligible population rate of 2.66%.

Statistical interim analysis and early stopping rules

No statistical interim analyses were planned or done. Patient recruitment stops when a total number of 130 patients have been included and finished their intervention or when the deadline August 31, 2022 is reached.

Timing of final analysis

The final analysis for the between group comparison (*Intervention group vs. Control comparator group*) for the primary endpoint (baseline, 4-, 8- and 12-weeks follow-up) is planned to be performed after the last randomised patient has completed the 12 weeks follow-up. The publication of the trial will be prepared when the data have been received and cleaned (anticipated by April 2023).

Timing of outcome assessments

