The reason for each crossover or withdrawal will be registered. Participants performing a crossover will remain in the study and be analysed following the intention-to-treat principle (i.e., remaining in their original group). The level of consent withdrawal will be classified as:

1. consent to continue follow-up and data collection;
2. consent to continue data collection only; or
3. complete withdrawal with no further follow-up and data collection (13).

In the CONSORT Flow Diagram numbers and reasons for withdrawal and/or loss to follow-up will be presented given at the 4-, 8- and 12-weeks (primary end point) outcome assessment; separately for the two intervention groups.

Baseline characteristics

The following data will be used to describe patients by randomisation group at baseline: mean age, height, weight, body mass index (BMI), smoking, alcohol consumption, highest education level, employment, index shoulder, dominant side affected, duration of shoulder symptoms, pain medication consumption due to shoulder related pain, depression, anxiety and outcome measures will be collected at baseline. The baseline characteristics are illustrated in [Table 1](#).

Categorical variables will be calculated and presented in numbers and percentages. While Means and Standard Deviations (SDs) will be calculated and presented for continuous variables if data follows a normal distribution; in case, continuous variables does not appear to follow normal distribution, median and interquartile range will be calculated. No tests of statistical significance will be conducted for baseline characteristics.

ANALYSIS

Primary outcome

Shoulder Pain and Disability Index (SPADI) [Time Frame: 0, 4, 8 and 12 weeks]

The primary outcome measure will be the between-group difference in change in SPADI-score ($\Delta\text{SPADI}_{12} = \text{SPADI}_{12\text{-weeks follow-up}} - \text{SPADI}_{\text{baseline}}$) from baseline to 12 weeks after initiating the treatment. SPADI is considered a valid, reliable, and responsive patient-reported questionnaire assessing shoulder pain and function, where each domain score is equally weighted and added to a total percentage score that ranges from 0 (best) to 100 (worst) (9,14) ([Figure 2](#)).

Key secondary outcomes

- *SPADI pain [Time Frame: 0, 4, 8 and 12 weeks]*

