A key secondary outcome will be the between-group difference in change in shoulder pain during sleep (Δ Pain during sleep₁₂ = Pain during sleep_{12-weeks follow-up} – Pain during sleep_{baseline}) from baseline to 12 weeks after initiating the treatment. The NRS is a valid, reliable and responsible single 11-item patient-reported pain scale that ranges from 0 (no pain) to 10 (worst pain) (22).

- *Shoulder pain during flexion/rotation/abduction [Time Frame: 0 and 12 weeks]*

A key secondary outcome will be the between-group difference in change in shoulder pain during flexion/rotation/abduction (Δ Pain during flex rot abd₁₂ = Pain during flex rot abd_{12-weeks follow-up} – Pain during flex rot abd_{baseline}) from baseline to 12 weeks after initiating the treatment. The NRS is a valid, reliable and responsible single 11-item patient-reported pain scale that ranges from 0 (no pain) to 10 (worst pain) (22).

The primary and key secondary outcomes will be presented as illustrated in **Table 2**.

Analysis methods

The CONSORT guideline (13) will be followed for all trial reporting aspects, as recommended by the “*Enhancing the QUAlity and Transparency Of health Research*” (EQUATOR) network website (23).

The primary (continuous) outcome will be analysed by using repeated measures mixed effects models, including participants as a random effect, with fixed effect factors for group (2 levels) and week (4 levels for the SPADI questionnaire [weeks 0, 4, 8, and 12]), the stratification factors and the interaction between group and week, adjusted for baseline values. To assess the adequacy of the linear models describing the observed data—and checking assumptions for the systematic and the random parts of the models—the model features will be investigated via the predicted values and the studentized residuals; that is, the residuals have to be normally distributed (around 0) and be independent of the predicted values. Results will be expressed based on least squares mean estimates with standard errors (SE) as well as the differences in the least squares means with 95% CIs to represent precision of the contrast between groups. Further, for the primary

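### The primary mixed model names no dependence between visits beyond a participant random effect, so the standard error of the 0-to-12-week contrast is too small if correlation fades over time

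*SAP*

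**What the plan says.** The abstract's Methods paragraph sets the general approach: "The continuous outcomes will be analysed based on Repeated-Measures Mixed Effects Models". The Analysis methods section gives the detail for the primary outcome:

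- Random part: "including participants as a random effect, with fixed effect factors for group (2 levels) and week".
- Visits in the outcome vector: "4 levels for the SPADI questionnaire [weeks 0, 4, 8, and 12".
- Remaining fixed terms: "the stratification factors and the interaction between group and week, adjusted for baseline values".
- Model check: "the residuals have to be normally distributed (around 0) and be independent of the predicted values".

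The Primary outcome section defines the target: "The primary outcome measure will be the between-group difference in change in SPADI-score", taken from baseline to week 12.

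The SAP names no residual covariance structure, random slope, robust standard error or degrees-of-freedom method. Its sensitivity analyses (baseline carried forward, per protocol, and the as-treated appendix table) change the imputation or the population, never the covariance. The section on additional analyses plans nothing further for the primary and key secondary outcomes.

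**The concern.** A participant random intercept with independent residuals has two variance parameters and treats every pair of visits as equally correlated. If repeated scores drift apart with time, the 4-week differences vary less than the 12-week difference. The model averages over all pairs and applies that average to the 12-week contrast, so its standard error is too small.

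At stake are the primary P value and confidence interval. The rule that reads an interval excluding differences above 4 SPADI points as absence of a clinically meaningful difference is also affected, because an interval that is too narrow meets it too easily. The same mechanism reaches the secondary outcomes measured at all four visits: SPADI pain, SPADI function, maximum pain, and pain in general activities, at rest and during sleep. The fixed testing sequence at 0.05 relies on their P values being valid.

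**Working it through.** **The plan's own figure.** Sample size and power considerations gives a difference of 8, SD 15.41, 65 per group, two-sided 0.05 and "statistical power of at least 85" percent. The standard error is 15.41 × √(2/65) = 2.70, so power is Φ(8/2.70 − 1.96) = 84.1% (83.6% with the noncentral t). That reproduces the stated power to within 2 points. It does not bear on this point, for which the SAP gives no figure except the nominal 5%.

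**Formula.** Take complete data, equal variance σ² at each visit and n per arm. Let r̄ be the mean of the six pairwise correlations and r(0,12) the correlation between baseline and week 12.

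- True variance of the group difference in change: 4σ²(1 − r(0,12))/n.
- Variance reported by the random-intercept model: 4σ²(1 − r̄)/n.
- SE ratio = √[(1 − r̄)/(1 − r(0,12))], and type I error = 2[1 − Φ(1.96 × ratio)].

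Example, correlations 0.8/0.7/0.6 at 4, 8 and 12 weeks apart: r̄ = (3×0.8 + 2×0.7 + 0.6)/6 = 0.733. The ratio is √(0.267/0.400) = 0.816 and the type I error is 11.0%.

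**Results** (every correlation is an assumption):

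| Correlation pattern | SE ratio | Type I error |
|---|---|---|
| Constant 0.6 | 1.000 | 5.0% |
| 0.7/0.68/0.66 | 0.960 | 6.0% |
| 0.8/0.77/0.75 | 0.935 | 6.7% |
| 0.7/0.65/0.6 | 0.913 | 7.4% |
| 0.7/0.6/0.5 | 0.856 | 9.3% |
| 0.8/0.7/0.6 | 0.816 | 11.0% |
| AR(1) 0.5 | 0.859 | 9.2% |
| AR(1) 0.6 | 0.833 | 10.3% |
| AR(1) 0.7 | 0.809 | 11.3% |
| AR(1) 0.8 | 0.786 | 12.4% |
| AR(1) 0.9 | 0.765 | 13.4% |

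Null simulation agrees. With 65 per arm, AR(1) 0.8 gave 12.4% and 0.8/0.7/0.6 gave 10.7%. With 16 per arm the same patterns gave 12.0% and 10.4%, so a smaller trial does not remove the problem. Adding the baseline covariate leaves the change contrast unchanged.

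**If only weeks 4, 8 and 12 are outcomes and baseline is a covariate,** still with a random intercept, the ratio is 0.844 to 0.948 and the type I error 6.3% to 9.8% across the fading patterns tried (AR(1) 0.6 to 0.9, 0.8/0.7/0.6, 0.7/0.6/0.5 and 0.7/0.65/0.6).

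**In SPADI points.** Assume 15.41 is the SD at each visit, with correlations 0.8/0.7/0.6 and 65 per arm. The true SE is 15.41 × √(4×0.400/65) = 2.42. The model reports 15.41 × √(4×0.267/65) = 1.97. The 95% half-widths are 1.96 × 2.42 = 4.7 and 1.96 × 1.97 = 3.9. An interval centred on zero would then pass the 4-point rule only because the SE is understated.

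**Check of the remedy.** Week-12 ANCOVA, used as the complete-data stand-in for an unstructured model, had a simulated type I error of 4.6% to 5.4% in every pattern tried. The unstructured model itself was not simulated.

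**Why baseline can be used only once.** With week 0 as both outcome and covariate, the week-0 residual is (1 − b) times the centred baseline, where b is the baseline coefficient. An unstructured covariance lets its variance shrink to zero as b approaches 1. With 130 women, each tenfold reduction in 1 − b adds 130 × ln 10 = 299 to the log-likelihood. In simulated data (65 per arm, AR(1) 0.7) it was −642 at b = 0.99, −43 at 0.9999 and +256 at 0.99999. There is no maximum.

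**The case against.** The strongest reply is that the SAP never says the participant effect is the sole dependence term and never writes compound symmetry. The SAS software it names can combine a participant effect with a residual structure. That is fair: a reader might infer that the sponsor chose a constant-correlation model, and the text does not establish this. It establishes that no other term is named. If another structure was intended it is unstated, and the same sentence resolves both cases.

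A reader might also infer that the primary test is known to run at 9% or more. The documents do not support that. They give no visit correlations, and AR(1) with 0.5 to 0.7 implies a baseline-to-week-12 correlation of only 0.125 to 0.343 (0.5³ to 0.7³). The women are 3 to 7 years past surgery, so a stable between-woman component, and hence mild fading, is at least as plausible.

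Larger figures arise if the week-12 least squares mean difference is taken from the model as written: about 10% to 15% under fading. Much of that belongs to a separate defect, the double use of week 0, which alone gives about 8% under constant correlation. It should not be charged to the covariance.

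Nor are all repeated secondary outcomes affected. A-ROM, P-ROM and pain during flexion, rotation or abduction are measured only at weeks 0 and 12, so there is one correlation and nothing to fade. Global perceived effect has three visits but no baseline, so these 0-to-12-week figures do not carry over to it.

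Finally, the Correction under the sample size section reports only 31 women from the Region of Southern Denmark. A richer covariance with five strata may then be hard to fit. That is a reason to prespecify a fallback. It does not justify leaving the structure unstated.

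**Conclusion.** The point holds as a conditional weakness in the primary analysis. Read literally, the model fixes one correlation for all visit pairs, and nothing planned would detect or correct a failure of that assumption: the residual checks concern normality and independence from predicted values. The type I error of the 0-to-12-week contrast is 5% under constant correlation, about 6-7% under mild fading and about 9-13% under AR(1)-type fading. These figures assume complete data and equal variances at each visit, and they omit the strata. Variances that change over time would alter them. The direction under fading correlation is firm, and the size is not known from the SAP. An inexpensive change removes the dependence on this assumption, so it is worth making before the data are analysed.

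**What to change.** In Analysis methods, replace the participant random effect with an unstructured within-participant covariance over visits, fitted by REML with Kenward-Roger degrees of freedom, and use baseline once. There are two ways to do this:

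- Keep weeks 4, 8 and 12 as outcomes with baseline SPADI as a covariate: 3×4/2 = 6 covariance parameters.
- Keep all four visits as outcomes and drop the baseline covariate: 4×5/2 = 10 covariance parameters.

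In the first option the primary estimate is the baseline-adjusted group difference at week 12. In the second it is the group difference in change from week 0 to week 12. Both come from the group-by-week terms. State in advance what happens if the fit does not converge, for example a simpler structure with robust standard errors, or ANCOVA at week 12. Apply the same text to the secondary outcomes measured at three or more visits.

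The cost is a short edit to the SAP, in software it already names. The downside is a few more covariance parameters than the two of a random intercept, and possible convergence trouble if recruitment stays small, which the fallback covers.
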